### 4.2.3.3 Pharmacodynamic Endpoints

Inhibition of BET proteins by MK-8628 leads to alterations in the transcription of messenger RNA (mRNA) at loci most sensitive to disruption of BET activity. These are considered target genes. Changes in expression, measured via mRNA, of prespecified target genes\* will be used as PD biomarkers to assess target engagement of BET proteins by MK-8628. (\*Note: the following non-exhaustive list of target genes may be considered for testing: *Bcl2*, *IL7R*, and *MYC* as down-regulated target genes; *CSRNP2*, *HEXIM1*, and *HIST1H2BK* as up-regulated target genes.) A range of PD biomarkers will be explored in surrogate samples from all subjects treated, using appropriate assays to establish target engagement. Rather than rely on gene expression changes in cancer cells, these PD biomarkers will be based on current PD knowledge from translational studies of mouse and human whole blood (e.g. Figure 4 below). Using RNA extracted from whole blood samples collected both prior to and following administration of MK-8628, messenger RNA transcript profiling may be performed to assess gene expression and evaluate whether changes in specific genes or sets of genes may represent a PD biomarker of response. Potential limitations of this assay include patient-to-patient variability and a small effect size of induction or repression upon treatment with MK-8628. Due to these limitations, the PD endpoint is considered to be qualitative given the assay may not be able to differentiate target engagement between the MK-8628 doses examined in this study.

[figure not shown]

Figure 4: Dose-dependent changes in BET protein target gene expression

*Dose-dependent changes in BET protein target gene expression in human whole blood ex vivo. Whole blood from 6 normal healthy volunteers was treated with either vehicle (0.1% dimethyl sulfoxide [DMSO]) or increasing concentrations of MK-8628. After 4 hours, whole blood was lysed (PAXgene tube) and mRNA extracted for quantitative polymerase chain reaction (qPCR) analysis of candidate BET target genes. Data were normalized ( $\Delta$ cycle threshold [Ct]) by peptidylpropyl isomerase B (PPIB) and plotted for all six individuals as change in  $\Delta$ Ct.*

#### **4.2.3.4 Efficacy Endpoints**

##### **4.2.3.4.1 Secondary Efficacy Endpoints: RECIST or PCWG -based Response Rate**

A secondary efficacy objective of this trial is to evaluate the anti-tumor activity of MK-8628 in subjects with selected advanced solid tumors (NMC, NSCLC, TNBC and CRPC). Secondary efficacy endpoints include (1) ORR, defined as the percentage of subjects who have achieved confirmed complete response (CR) or partial response (PR) according to Response Evaluation Criteria in Solid Tumors (RECIST) v1.1 (see Section 12.8) or Prostate Cancer Clinical Trials Working Group (PCWG2) (see Section 12.9), as assessed by investigator radiologic review; (2) DOR, defined as the time from first documented evidence of CR or PR until disease progression or death due to any cause, whichever occurs first; and (3) DCR, defined as the percentage of subjects who have achieved stable disease or confirmed complete response (CR) or confirmed partial response (PR) according to RECIST v1.1 or PCWG2, by the investigator review

##### **4.2.3.4.2 Exploratory Efficacy Endpoints**

Exploratory efficacy endpoints include (1) PFS, defined as the time from allocation to the first documented disease progression according to RECIST v1.1 or PCWG2 as assessed by investigator radiologic review, or death due to any cause, whichever occurs first, and (2) OS.

##### **4.2.3.5 Planned Exploratory Biomarker Research**

###### **Planned Genetic Analysis**

Understanding genetic determinants of drug response is an important endeavor during medical research. This research will evaluate whether genetic variation within a clinical trial population correlates with response to the treatment(s) under evaluation. If genetic variation is found to predict efficacy or adverse events, the data might inform optimal use of therapies in the patient population. This research contributes to understanding genetic determinants of efficacy and safety associated with the treatments in this study.

##### **4.2.3.6 Future Biomedical Research**

The Sponsor will conduct Future Biomedical Research on specimens collected for future biomedical research during this clinical trial. This research may include genetic analyses (DNA), gene expression profiling (RNA), proteomics, metabolomics (serum, plasma) and/or the measurement of other analytes.

Such research is for biomarker testing to address emergent questions not described elsewhere in the protocol (as part of the main trial) and will only be conducted on specimens from appropriately consented subjects. The objective of collecting specimens for Future Biomedical Research is to explore and identify biomarkers that inform the scientific understanding of diseases and/or their therapeutic treatments. The overarching goal is to use such information to develop safer, more effective drugs/vaccines, and/or to ensure that subjects receive the correct dose of the correct drug/vaccine at the correct time. The details of this Future Biomedical Research sub-trial are presented in Section 12.2 - Collection and Management of Specimens for Future Biomedical Research. Additional informational

material for institutional review boards/ethics committees (IRBs/ERCs) and investigational site staff is provided in Section 12.3.

### **4.3 Benefit/Risk**

Subjects in clinical trials generally cannot expect to receive direct benefit from treatment/vaccination during participation, as clinical trials are designed to provide information about the safety and effectiveness of an investigational medicine.

Additional details regarding specific benefits and risks for subjects participating in this clinical trial may be found in the accompanying Investigators Brochure (IB) and Informed Consent documents.

## **5.0 METHODOLOGY**

### **5.1 Entry Criteria**

#### **5.1.1 Diagnosis/Condition for Entry into the Trial**

Male/Female subjects with non-small cell lung cancer, triple negative breast cancer or castration-resistant prostate cancer of at least 18 years of age, and male/female subjects with NUT midline carcinoma of at least 16 years of age will be enrolled in this trial.

#### **5.1.2 Subject Inclusion Criteria**

In order to be eligible for participation in this trial, the subject must:

1. Have signed informed consent/assent prior to initiation of any study-specific procedures and treatment. For study subjects who are legal minors, the parent or legal guardian must also sign the consent/assent form. The subject may also provide consent/assent for Future Biomedical Research. However, the subject may participate in the main trial without participating in Future Biomedical research.
2. Have histologically or cytologically confirmed diagnosis of one of the following advanced or metastatic solid tumors for which standard therapy either does not exist or has proven ineffective, intolerable or unacceptable for the subject:
  - a) NUT midline carcinoma (NMC)(ectopic expression of NUT protein as determined by IHC and/or detection of BRD-NUT gene translocation as determined by FISH)
  - b) Non-small cell lung cancer (NSCLC): all comers without gene rearrangement or mutational restrictions
  - c) Triple negative breast cancer (TNBC) defined according to ASCO recommendations [50][51]
  - d) Castration-resistant prostate cancer (CRPC)
3. Have at least one measurable lesion as per RECIST version 1.1., except for CRPC subjects who may be enrolled with objective evidence of disease as per Prostate Cancer Clinical Trials Working Group (PCWG2) criteria.

4. For NSCLC, TNBC and CRPC subjects, be age  $\geq 18$  years at the time of informed consent; for NMC subjects, be age  $\geq 16$  years at the time of informed consent.
5. Have a life expectancy  $\geq 3$  months.
6. Have an Eastern Cooperative Oncology Group (ECOG) Performance Status (PS)  $\leq 1$ .
7. Demonstrate adequate organ function (adequate bone marrow reserve, renal and liver function) as defined in Table 1. (Note: All screening labs should be performed within 10 days of treatment initiation).

Table 1: Adequate Organ Function Laboratory Values

System	Laboratory Value
Hematological	
Absolute neutrophil count (ANC)	$\geq 1.5 \times 10^9/L$
Platelets	$\geq 150 \times 10^9/L$
Hemoglobin	$\geq 9.0$ g/dL *Note: subject must not have had a blood transfusion within 7 days of screening in meeting this criteria
Renal	
Creatinine clearance	$\geq 30$ mL/min calculated according to the Cockcroft and Gault formula or Modification of Diet in Renal Disease (MDRD) formula for subjects aged $> 65$ years (see Section 12.5)
Hepatic	
Total bilirubin	$\leq 1.25$ X upper limit of normal (ULN) OR In case of liver involvement, $\leq 2$ x ULN will be allowed
Aspartate aminotransferase (AST) (SGOT) and alanine aminotransferase (ALT) (SGPT)	$< 3$ X ULN
Alkaline Phosphatase	If $> 2.5$ X ULN, then liver fraction should be $\leq 2.5$ X ULN
Chemistry	
Serum albumin	For NSCLC, CRPC and TNBC: $\geq 3.0$ g/dL
	For NMC: $\geq 2.0$ g/dL
Coagulation	
International Normalized Ratio (INR)	$\leq 1.5$

8. Have an interval of  $\geq 3$  weeks (or  $\geq 2$  weeks for NMC patients) since chemotherapy ( $\geq 6$  weeks for nitrosoureas or mitomycin C), immunotherapy, hormone therapy or any other anticancer therapy (including investigational) or surgical intervention resection, or  $\geq 3$  half-lives for monoclonal antibodies, or  $\geq 5$  half-lives for other non-cytotoxic agents (whichever is longer).

9. CRPC subjects must maintain ongoing androgen deprivation therapy with a gonadotropin releasing hormone (GnRH) analogue, antagonist or orchiectomy providing serum testosterone is < 50 ng/dL (<1.7 nmol/L).
10. Subjects receiving bisphosphonate or denosumab therapy must be on stable doses for at least 4 weeks before initiating study treatment
11. Female subjects of childbearing potential must have a negative urine or serum pregnancy test within 72 hours prior to receiving the first dose of study medication. If the urine test is positive or cannot be confirmed as negative, a serum pregnancy test will be required.
12. Female subjects of childbearing potential should be willing to use an adequate method of contraception as outlined in section 5.7.3– Contraception, for the course of the study through 90 days after the last dose of study medication. Note: Abstinence is acceptable if this is the usual lifestyle and preferred contraception for the subject.
13. Male subjects of childbearing potential must agree to use an adequate method of contraception as outlined in Section 5.7.3 – Contraception, starting with the first dose of trial treatment through 90 days after the last dose of study medication. Note: Abstinence is acceptable if this is the usual lifestyle and preferred contraception for the subject.

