### 8.1 Statistical Analysis Plan Summary

Key elements of the statistical analysis plan are summarized below; the comprehensive plan is provided in subsequent sections.

Study Design Overview	A Phase IB Dose Exploration Trial with MK-8628, a Small Molecule Inhibitor of the Bromodomain and Extra-Terminal (BET) Proteins, in Subjects with Selected Advanced Solid Tumors
Treatment Assignment	This is an open label study with dose level specific cohorts.
Analysis Populations	Efficacy: Treatment Full Analysis Set (FAS), which is the same as ASaT Safety: DLT evaluable, and All Subjects as Treated (ASaT)
Primary Endpoint(s)	Proportion of subjects experiencing at least one DLT in cycle 1 (day 1 to 21)
Secondary Endpoints	ORR, DOR and DCR based on the best overall response from tumor evaluations performed every 2 cycles, according to RECIST v1.1 or PCWG2 as assessed by investigator radiologic review.
Statistical Methods for Key Efficacy/Immunogenicity/ Pharmacokinetic Analyses	ORR and DCR will be estimated using an exact method based on the binomial distribution (Clopper-Pearson interval).
Statistical Methods for Key Safety Analyses	Counts and percentage of DLT will be provided. 80% Bayesian credible interval for DLT rate will be estimated based on a prior distribution of Beta(1,1).
Interim Analyses	During the dose escalation phase, regular assessment of data from the most recent cohort of subjects evaluable for DLT will be performed.
Multiplicity	This is an estimation study and no multiplicity adjustment will be implemented
Sample Size and Power	The study is designed to assess the safety of MK-8628 in subjects with advanced or metastatic solid tumors. The small numbers per cohort are not intended for statistical hypotheses.  Up to 72 evaluable subjects (up to 6-14 per three dose levels in the dose escalation part [Part A] and up to 30 in the NMC cohort [Part B]) will be included. The final sample size will depend on the number of subjects experiencing DLTs at each DL, and may be increased if the RP2D is not reached and additional DLs are required.

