### **8.4.2 Efficacy/Pharmacokinetics/Pharmacodynamics Endpoints**

Secondary endpoints are presented below:

**Objective Response Rate (ORR):** is defined as the percentage of subjects who have achieved confirmed complete response (CR) or partial response (PR) according to RECIST v1.1 or PCWG2 as assessed by investigator radiologic review.

**Duration of Response (DOR):** is defined as the time interval between the date of the first confirmed response (CR/PR) (the response prior to confirmation) and the date of first documented disease progression based upon RECIST v1.1 or PCWG2 as assessed by investigator radiologic review.

**Disease Control Rate (DCR):** is defined as the percentage of subjects who have achieved stable disease or confirmed complete response (CR) or confirmed partial response (PR) according to RECIST v1.1 or PCWG2 as assessed by investigator radiologic review. Subjects with missing response will be considered not to have achieved disease control.

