## **8.5 Analysis Populations**

### **8.5.1 Efficacy Analysis Populations**

Treatment **Full Analysis Set (FAS)**, also known as **evaluable for efficacy**: subjects who receive at least one dose of study drug.

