### 12.8.3 Definition of Best Overall Tumor Response

The best overall response is the best response recorded between the start and the end of treatment, as described below. Overall response is calculated for each assessment time point according to [Table 17](#).

Table 17: Overall response in subjects with target (+/- non-target) disease

Target lesions	Non-target lesions	New lesions	Overall response
CR	CR	No	CR
CR	Non-CR/non-PD	No	PR
CR	Not evaluated	No	PR
PR	Non-PD or not all evaluated	No	PR
SD	Non-PD or not all evaluated	No	SD
Not all evaluated	Non-PD	No	NE
PD	Any	Yes or No	PD
Any	PD	Yes or No	PD
Any	Any	Yes	PD

CR, complete response; PR, partial response; SD, stable disease; PD, progressive disease; NE, not evaluable

The best overall response is determined once all data for a given subject are available. [Table 18](#) below summarizes the best overall tumor response.

Table 18: Best overall response

Overall response First time point	Overall response Subsequent time points	Best overall response
CR	CR	CR
CR	PR	SD, PD or PR 
CR	SD	SD provided minimum criteria for SD duration met, otherwise, PD
CR	PD	SD provided minimum criteria for SD duration met, otherwise, PD
CR	NE	SD provided minimum criteria for SD duration met, otherwise NE
PR	CR	PR
PR	PR	PR
PR	SD	SD
PR	PD	SD provided minimum criteria for SD duration met, otherwise, PD
PR	NE	SD provided minimum criteria for SD duration met, otherwise NE
NE	NE	NE

CR, complete response; PR, partial response; SD, stable disease; PD, progressive disease; NE, not evaluable

1. If a CR is truly met at first time point, then any disease seen at a subsequent time point, even disease meeting PR criteria relative to baseline, makes the disease PD at that point (since disease must have reappeared after CR). Best response would depend on whether minimum duration for SD was met. However, sometimes CR may be claimed when subsequent scans suggest small lesions were likely still present and in fact the subject had PR, not CR at the first time point. Under these circumstances, the original CR should be changed to PR and the best response is PR.

Subjects with a global deterioration of health status requiring discontinuation of treatment without objective evidence of disease progression at that time should be reported as “symptomatic deterioration”. Every effort should be made to document the objective progression even after discontinuation of treatment.

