### **12.9.3 Bone**

Given the frequency of bone involvement in patients with progressive, castration-resistant disease, the decreased emphasis of early changes in PSA, and the increased availability of cytostatic agents, reliable methods to assess changes in bone are of increasing importance. PCWG2 recognizes that standards for using MRI and positron emission tomography (PET) to assess bone metastases are under active investigation, so only radionuclide bone scans are considered here. PCWG2 also recognizes that there are no validated criteria for response on radionuclide bone scan.

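### ORR counts CRPC subjects who may enter without measurable disease and have no defined route to a response, so it is diluted by their share; how they enter DCR is left undefined.

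*Combined protocol and SAP*

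**What the plan says.** Section 5.1.2, criterion 3, asks for at least one lesion measurable by RECIST 1.1, "except for CRPC subjects who may be enrolled with objective evidence of disease as per Prostate Cancer Clinical Trials Working Group (PCWG2) criteria". NMC, NSCLC and TNBC subjects have no such exemption.

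Section 8.1 gives the analysis set: "Efficacy: Treatment Full Analysis Set (FAS), which is the same as ASaT". Section 8.5.1 defines it as "subjects who receive at least one dose of study drug", with no condition on measurable disease.

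Section 8.4.2 defines ORR as the "percentage of subjects who have achieved confirmed complete response (CR) or partial response (PR) according to RECIST v1.1 or PCWG2", on the investigator's radiologic review. DCR adds stable disease to the successes, and one rule covers absent data: "Subjects with missing response will be considered not to have achieved disease control".

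For bone, Section 12.9.3 states that "PCWG2 also recognizes that there are no validated criteria for response on radionuclide bone scan", and Table 19 records the outcome only as new lesions or no new lesions. If visible bone lesions disappear, which the section calls rare, this is to be confirmed at the next assessment, but it is not assigned to a response category.

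In Section 12.8, Table 16 has categories for non-target lesions: CR, non-CR/non-PD and PD. Table 17, the only table that turns lesion findings into an overall response, is titled "Overall response in subjects with target (+/- non-target) disease". Table 18 makes stable disease depend on a minimum duration, which is not stated.

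Section 8.6 presents data by dose level and, where appropriate, by indication. Section 8.9 pools Parts A and B at each dose level for efficacy. Part B takes NMC subjects only (2.1).

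**The concern.** The denominator admits subjects for whom the response criteria define no success. A CRPC subject with bone-only disease has no lesion sum that could shrink by 30%, so PR is out of reach. Disappearance of bone lesions is not linked to CR. Because ORR rests on radiologic review, a fall in PSA cannot count either.

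The reported ORR then depends on case mix as well as on drug activity. This matters most in comparisons between dose levels. CRPC subjects start only at 20, 30 or 40 mg BID (Part A). A starting dose of 10 mg BID occurs only in Part B, where every subject has NMC and must have a measurable lesion. Allocation follows open slots (5.3) without stratification (5.4), so nothing balances tumour type across doses. ORR is part of the secondary antitumour objective (3.2), and early efficacy is one input to the RP2D decision (5.2.1.5).

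For DCR, the plan does not say whether no new lesions, or non-CR/non-PD, is stable disease, not evaluable or missing. In an open-label trial that coding could be settled after the outcomes are known.

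**Working it through.** **1. The plan's own figure.** Section 8.6.1 specifies 95% Clopper-Pearson intervals. For x responders in n, the lower limit is the 0.025 quantile of Beta(x, n−x+1) and the upper limit is the 0.975 quantile of Beta(x+1, n−x). For 3 in 14 this gives 0.214 (0.047, 0.508), as in Table 13. All 11 rows of that column reproduce to three decimals.

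**2. Dilution formula.** Let N be the treated subjects in a reporting row, m those with CRPC and no route to response, and p the true ORR among the rest. The expected all-treated ORR is p × (N−m)/N, so the relative loss is m/N. This assumes that the m subjects contribute no responses.

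**3. Expected size at N=14.** The documents do not give m, so a range is assumed.

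| m | m/N | Expected ORR if p=20% | Expected ORR if p=30% |
|---|---|---|---|
| 0 | 0% | 20.0% | 30.0% |
| 2 | 14.3% | 17.1% | 25.7% |
| 4 | 28.6% | 14.3% | 21.4% |
| 7 | 50.0% | 10.0% | 15.0% |

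Two dose levels with the same p=20%, one with m=0 and one with m=4, would differ by 20.0 − 14.3 = 5.7 percentage points with no difference in activity. Where Part B adds NMC subjects to a dose level, N grows and m does not, so m/N changes again for reasons of enrolment.

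**4. Observed rates with 3 responders in 14 treated.**

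| Denominator | ORR | 95% CI |
|---|---|---|
| All treated, 3/14 | 21.4% | 4.7% to 50.8% |
| Measurable only, m=2, 3/12 | 25.0% | 5.5% to 57.2% |
| Measurable only, m=4, 3/10 | 30.0% | 6.7% to 65.2% |
| Measurable only, m=7, 3/7 | 42.9% | 9.9% to 81.6% |

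**5. DCR under different codings.** Assume 14 subjects: 10 with measurable disease, of whom 5 are controlled, and 4 bone-only. The rate among measurable subjects is 5/10 = 50.0%.

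| Bone-only subjects counted as controlled | DCR | 95% CI |
|---|---|---|
| 0 | 5/14 = 35.7% | 12.8% to 64.9% |
| 2 | 7/14 = 50.0% | 23.0% to 77.0% |
| 3 | 8/14 = 57.1% | 28.9% to 82.3% |
| 4 | 9/14 = 64.3% | 35.1% to 87.2% |

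The all-treated DCR can fall below, equal or exceed the measurable-only rate. The text does not say which coding applies.

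**The case against.** The strongest reply has four parts.

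First, ORR in all treated subjects is a defined and conservative quantity, not a faulty estimate of something else. That is fair, and it is a reason to keep the rate as supportive. It does not make the rate comparable between dose levels with different tumour mixes.

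Second, results by indication (8.6) would confine the effect to CRPC rows. This is true of those rows, but it concentrates the dilution there, because m is then divided by the CRPC count alone. The dose-level rows still carry it.

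Third, disease that is not measurable is not always bone-only. Non-measurable soft-tissue disease has a CR category in Table 16. This stands at lesion level, but Table 17 has no row that converts it into an overall response. If an investigator assigned CR without such a row, the dilution would be smaller than m/N.

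Fourth, the consequence is limited. Section 8.3 states no hypotheses, Section 5.2.1.5 makes the DLT rate the driver of dose selection with other facets supportive, and CRPC activity is also followed through mandatory PSA. All of this stands. The intervals in step 4 also overlap heavily.

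A reader might go further and infer that bone-only subjects also count as DCR failures, so that both rates are biased down. The documents do not support that. Section 8.4.2 makes only a missing response a failure. A subject scanned on schedule and recorded as having no new lesions has an assessment, and no text classes it as missing. Equally, no text classes it as stable disease.

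**Conclusion.** The point holds for ORR. Following the plan as written, ORR is diluted by m/N, where m is the number of treated CRPC subjects whose disease has no defined route to CR or PR. With 3 responders in 14, the gap is 21.4% against 25.0% for m=2 and 30.0% for m=4. These values of m are assumptions; if m is zero nothing changes. Because CRPC enters only through Part A, the dilution can vary by dose level independently of the drug.

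For DCR the finding is an undefined mapping of unknown direction, together with a minimum duration of stable disease that Table 18 invokes and nowhere gives. No downward bias is shown.

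The practical impact is modest. These are secondary estimates with wide intervals and no test, and efficacy is supportive for the RP2D. The change is worth making because it is cheap and should be settled before the data are read.

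**What to change.** - **ORR (8.4.2, 8.5.1).** Report ORR in treated subjects with measurable disease at baseline, keep the all-treated rate as supportive, and show CRPC subjects without measurable disease on a separate line.
- **Overall response (12.8.3).** Add a table for subjects with non-target disease only, and state how the bone-scan outcomes of Table 19 feed into it.
- **DCR (8.4.2).** State whether no new lesions and non-CR/non-PD count as stable disease, not evaluable or missing, and give the minimum duration that Table 18 requires. Without a duration, counting every scan with no new lesions as disease control could push DCR upwards.

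Settle all three before database lock. Section 8.0 already allows changes to non-confirmatory analyses to be documented in the supplemental SAP. The cost is wording: screening imaging already shows who has measurable disease, so no new data are needed. The downside is a smaller ORR denominator and wider intervals. In the example with m=4, the interval widens from 50.8 − 4.7 = 46.1 to 65.2 − 6.7 = 58.5 percentage points.
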